4.1.4 Selection and Timing of Dose for Each Subject

4.1.4.1 Nivolumab

Cohort A

- Nivolumab will be administered at a dose of 240 mg as an intravenous infusion over 30 minutes on Day 15 during Cycle 1, and on Days 1 and 15 during Cycles 2 through 6 (ie, every 2 weeks of each 28-day cycle). Starting Cycle 7 and beyond, nivolumab will be administered at a dose of 480 mg as an IV infusion over 30 minutes every 4 weeks (Day 1 of each 28-day cycle).
- Nivolumab can be delayed within a 3-day window of Day 1 and Day 15, during Cycles 1 through 6, as long as the 12-day interval between 2 nivolumab doses is respected. During Cycles 7 and beyond, nivolumab can be delayed within a week, as long as the 21-day interval between 2 nivolumab doses is respected. Doses that fall outside the allowed window should be skipped.

Cohort B

- Patients randomized to ND treatment (only): nivolumab will be administered at a dose of 240 mg as an intravenous infusion over 30 minutes on Day 15 of Cycle 1. Starting Cycle 2 and beyond, nivolumab will be administered at a dose of 480 mg as an intravenous infusion over 30 minutes every 4 weeks (Day 1 of each 28 day cycle).
- Cycle 1 dose (C1D15) can be delayed within a 3 day window from Day 15. Doses that fall outside the allowed window should be skipped.
- From Cycle 2 (C2D1) and beyond, nivolumab can be delayed within in a 7 day window of Day 1, as long as the 21-day interval between two 480 mg nivolumab doses is respected, and a 12-day interval between C1D15 and C2D1 is respected. Doses that fall outside the allowed window should be skipped.

Nivolumab should be administered before daratumumab. There are no pre-medications recommended for nivolumab.

Subjects should be carefully monitored for infusion reactions during nivolumab administration. If an acute infusion reaction is noted, subjects should be managed according to [Section 3.4.2.1](#).

There will be no dose escalations or reductions of nivolumab allowed. Doses of nivolumab may be interrupted, delayed, or discontinued depending on how well the subject tolerates the treatment.

4.1.4.2 Daratumumab

Daratumumab will be administered at a dose of 16 mg/kg as an IV infusion every week (Days 1, 8, 15, and 22 of each 28-day cycle) during Cycles 1 and 2. As an option, in Cycle 1, the first full dose of daratumumab at 16 mg/kg may be split into 2 doses at 8 mg/kg and administered via IV on Cycle 1 Days 1 and 2. From Cycles 3 through 6, daratumumab will be administered every 2 weeks (Days 1 and 15 of each 28-day cycle), then starting Cycle 7 and beyond, daratumumab will be administered every 4 weeks (Day 1 of each 28-day cycle). The infusion rates should closely follow the specifications of the currently approved (USPI)/pharmacy reference manual.⁹⁸

All infusions will be planned as outpatient visits. Subjects will receive preinfusion medications and postinfusion medications as detailed in the protocol.

Daratumumab should be administered after nivolumab.

MM subjects randomized to the ND or D regimens will receive pre- and post-infusion medication for daratumumab infusion per the daratumumab label, as described (in [Section 3.4.1.4](#)).

MM subjects randomized to ND-Pd regimen will receive the treatment regimen dexamethasone dose split as IV pre-infusion and oral post-infusion on weeks with daratumumab infusions, and only oral in the weeks without daratumumab infusion (see [Section 4.1.4.4](#)). No additional corticosteroids besides the dexamethasone dose included in the treatment regimen will be administered to the ND-Pd subjects.

The dilution volumes and infusion rates for C1D1 (16 mg/kg), and optional split-dosing of C1D1 (8 mg/kg) and C1D2 (8 mg/kg), C1D8 (16 mg/kg), and subsequent infusions are provided in [Table 4.1.4.2-1](#). The sponsor may modify the infusion rates or the preinfusion medications prospectively based upon the information collected to date from this and other studies. Additional details for administration times and rates, as well as preinfusion medications, will be provided in the administration guidelines (study site investigational product and procedures manual/package insert).

Table 4.1.4.2-1: Daratumumab Infusion Rates

	Dilution Volume	Initial Infusion Rate (first hour)	Increments of Infusion Rate	Maximum Infusion Rate
C1D1 (16 mg/kg single dose)	1000 mL	50 mL/hour	50 mL/hour every hour	200 mL/hour
Optional split-dosing: C1D1 and C1D2 (8 mg/kg split dose)	500 mL	50 mL/hour	50 mL/hour every hour	200 mL/hour

Table 4.1.4.2-1: Daratumumab Infusion Rates

	Dilution Volume	Initial Infusion Rate (first hour)	Increments of Infusion Rate	Maximum Infusion Rate
C1D8 ^{a,b} (16 mg/kg)	500 mL	50 mL/hour	50 mL/hour every hour	200 mL/hour
Subsequent infusions ^c	500 mL	100 mL/hour	50 mL/hour every hour	200 mL/hour

^a If the subject's first infusion of daratumumab at 16 mg/kg is well-tolerated, subsequent infusions will be administered at an initial rate of 100 mL/hour and increased by 50-mL/hour increments at 60-minute intervals, as tolerated, to a maximum rate of 200 mL/hour.

^b If the subject's first 2 infusions of 8 mg/kg daratumumab are well-tolerated (defined as an absence of IRR >Grade 1), the first infusion of 16 mg/kg daratumumab will be administered at an initial rate of 50 mL/hour and increased by 50-mL/hour increments at 60-minute intervals, as tolerated, to a maximum rate of 200 mL/hour. If the 8 mg/kg infusions are not well-tolerated (defined as IRR >Grade 1), the dose on C1D8 should be given in 1000 mL.

^c Modified rates should only be used if the first 2 16 mg/kg infusions of daratumumab were well-tolerated as defined by an absence of > Grade 1 infusion-related reactions during a final infusion rate of ≥ 100 mL/hr

Vital signs should be monitored extensively throughout daratumumab infusion(s) on Cycle 1 Day 1 (16 mg/kg) or Cycle 1 Days 1 & 2 (split-dosing at 8 mg/kg). For subsequent infusions, vital signs should be measured before the start of the infusion and at the end of the infusion. If a subject experiences any significant medical event, then the investigator should assess whether the subject should stay overnight for observation. If the subject has not experienced a significant medical event but is hospitalized overnight only for observation, then the hospitalization should not be reported as a serious adverse event.

There will be no dose escalations or reductions of daratumumab allowed. Doses of daratumumab may be interrupted, delayed, or discontinued depending on how well the subject tolerates the treatment.

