4.1.1.2 Daratumumab

Daratumumab injection for IV infusion is considered IMP for this study. Daratumumab vials must be stored in accordance with the package insert (USPI) /clinical supply labeling.⁷⁰

Daratumumab is an immunoglobulin G1 kappa (IgG1 κ) human monoclonal antibody against CD38 antigen, produced in a mammalian cell line (Chinese Hamster Ovary [CHO]) using recombinant DNA technology. The molecular weight of daratumumab is approximately 148 kDa.

Daratumumab is supplied as a colorless to pale yellow preservative-free solution for intravenous infusion in single-dose vials. Daratumumab must be diluted with 0.9% Sodium Chloride Injection, USP and to be administered as IV infusion according to the infusion rates specified in the (USPI)/pharmacy reference manual.⁷⁰

Daratumumab can cause severe infusion reactions, where about half of all patients in the studies to date experienced a reaction, most during the first infusion. Infusion reactions can also occur with subsequent infusions. Nearly all reactions occurred during infusion or within 4 hours of completing the daratumumab infusion.

Because of this high risk of infusion related reactions daratumumab infusions will be administered per the approved (USPI)/pharmacy reference manual⁷⁰ by a healthcare professional, with immediate access to emergency equipment and appropriate medical support to manage infusion reactions if they occur, and all subjects will receive pre-infusion and post-infusion medication per the approved (USPI)/pharmacy reference manual.⁷⁰

Before administration the drug product should be stored and prepared as per the instructions in current (USPI)/pharmacy reference manual.⁷⁰ The dose of daratumumab to be administered to a

subject will be calculated by multiplying the subject's weight (kg) by 16 mg/kg. The subject's predose weight on Day 1 of each cycle will be used to calculate the dose for each cycle. The dose does not need to be recalculated for weight changes that are < 10% from baseline. Each dose should be infused as per instructions in the current daratumumab (USPI)/pharmacy reference manual.⁷⁰

For the administration of the first 16 mg/kg dose of daratumumab, in addition to previously approved single first infusion on Cycle 1 Day 1, a split-dosing regimen (ie, splitting the first dose over two consecutive days at 8 mg/kg on Cycle 1 Days 1 and 2) was recently approved in EU, US, and Canada. Investigators are allowed to opt for the split-dosing regimen.

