4.1.3 Study Drug Storage, Preparation and Administration

Please refer to the current version of the IB and/or pharmacy reference sheets for complete storage, handling, dispensing, and infusion information for nivolumab, and to the current (USPI)/pharmacy reference manual⁹⁸ for daratumumab, and dexamethasone IV.

Nivolumab vials must be stored at a temperature of 2° to 8°C and should be protected from light and freezing. If stored in a glass front refrigerator, vials should be stored in the carton. Recommended safety measures for preparation and handling of nivolumab include laboratory coats and gloves. For details on prepared drug storage and use time of nivolumab under room temperature/light and refrigeration, please refer to the nivolumab IB section for “Recommended Storage and Use Conditions” and/or pharmacy reference sheets.

Nivolumab injection is to be administered as an IV infusion through a 0.2-micron to 1.2-micron pore size, low-protein binding polyethersulfone membrane in-line filter at the protocol-specified doses. It is not to be administered as an IV push or bolus injection. Nivolumab injection can be infused undiluted (10 mg/mL) or diluted with 0.9% Sodium Chloride Injection, USP or 5% Dextrose Injection, USP to protein concentrations as low as 1 mg/mL. Care must be taken to assure sterility of the prepared solution as the product does not contain any antimicrobial preservative or bacteriostatic agent.

Daratumumab infusion solution will be prepared as a 1,000-mL (first dose, unless using split dose) or 500-mL (second and subsequent doses) dilution of daratumumab in sterile, pyrogen-free 0.9% Sodium Chloride Injection, USP. Preparation of infusion bags should be done on the day of the planned infusion. Daratumumab must be administered as an IV infusion given through a well-functioning IV catheter by using an infusion pump or syringe pump. Daratumumab must be filtered by using an inline filter (0.2 µM) during the infusion. Manuals with detailed descriptions for preparation and administration of daratumumab will be supplied to each pharmacy and site.

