In addition to administering a full dose of 16 mg/kg on Cycle 1 Day 1, “split-dosing” of daratumumab (ie, 8 mg/kg on Cycle 1 Day 1 and 8 mg/kg on Cycle 1 Day 2) can be utilized for Cohort B at the investigator’s discretion. The first split-dose infusion will be prepared as a 500-mL dilution of 8 mg/kg of daratumumab given on Days 1 and 2 of Cycle 1. If these 2 infusions are well-tolerated (absence of > Grade 1 IRR), the second week of daratumumab will be given as a 16 mg/kg dose diluted in 500 cc of normal saline. If the first 2 doses of daratumumab are not well-tolerated (defined as > Grade 1 IRR), then the second week of daratumumab will be given as 16 mg/kg in 1000 mL on Cycle 1 Day 8. From Cycle 1 Day 15 and beyond, the dose of daratumumab will not be split and will be the standard 16-mg/kg dose. The dilution will be in 1000 cc of normal saline until the subject completes an infusion without > Grade 1 IRR. For all infusions, daratumumab will be prepared in sterile, pyrogen free 0.9% NaCl. Preparation of the infusion bags should be done on the day of the planned infusion. Daratumumab must be administered as an IV infusion given through a well-functioning IV catheter by using an infusion pump. The study drug must be filtered by using an inline filter (0.2 µM) during the infusion. Manuals with detailed descriptions for preparation and administration of daratumumab will be supplied to each pharmacy and site.

Infusion-related supplies (eg, IV bags, in-line filters, 0.9% NaCl solution, pump) will not be supplied by the sponsor and should be purchased locally if permitted by local regulations.

When more than one study drugs are to be administered as IV infusion on the same day, separate infusion bags and filters must be used for each infusion. Nivolumab is to be administered first. The nivolumab infusion must be promptly followed by a saline flush to clear the line of nivolumab before starting the daratumumab infusion. The second infusion will always be daratumumab and will start no sooner than 30 minutes after completion of the nivolumab infusion.

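### Table 4.1.4.2-1 gives two rules for starting daratumumab at 100 mL/hour, and they clash when the first full dose is tolerated and the second is not

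*Protocol*

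**What the plan says.** Protocol Section 4.1.4.2 sends sites to Table 4.1.4.2-1 for dilution volumes and rates. The C1D8 row (500 mL) starts at 50 mL/hour and carries footnotes a and b. The row for subsequent infusions (500 mL) starts at 100 mL/hour and carries footnote c. Both rows step up by 50 mL/hour each hour to a maximum of 200 mL/hour.

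- Footnote a: "If the subject's first infusion of daratumumab at 16 mg/kg is well-tolerated, subsequent infusions will be administered at an initial rate of 100 mL/hour".
- Footnote b, for subjects who tolerated the two 8 mg/kg split doses: "the first infusion of 16 mg/kg daratumumab will be administered at an initial rate of 50 mL/hour". Under split dosing, C1D8 is therefore the first 16 mg/kg infusion.
- Footnote c: "Modified rates should only be used if the first 2 16 mg/kg infusions of daratumumab were well-tolerated". It defines tolerance as no infusion-related reaction above Grade 1 during a final rate of at least 100 mL/hour. Footnote a gives no definition.

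The text introducing the table lists C1D8 apart from later infusions: "C1D8 (16 mg/kg), and subsequent infusions are provided in" the table. The protocol also defers to an outside document, in Section 4.1.4.2 ("The infusion rates should closely follow the specifications of the currently approved (USPI)/pharmacy reference manual") and in Section 4.1.1.2 ("Each dose should be infused as per instructions in the current daratumumab (USPI)/pharmacy reference manual").

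**The concern.** Footnote a needs one tolerated 16 mg/kg infusion before the faster start; footnote c needs the first two. Where a subject meets the first condition and not the second, a site cannot obey both.

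The clearest case is also the least comfortable one. A single-dose subject tolerates C1D1 and then reacts at C1D8, which started at 50 mL/hour. Footnote a would have the next infusion start at twice that rate. Section 4.1.1.2 says that about half of patients in studies to date had a reaction, mostly at the first infusion, and that later infusions can also cause one. Section 3.4.1.4 slows an infusion after a reaction: if it is resumed, the rate is at most half that at which the reaction occurred. Cohort B is open to enrollment and both its arms receive daratumumab, so the instruction is live.

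**Working it through.** **Step 1. Trace both footnotes through the early infusions.** 'Tolerated' means no reaction above Grade 1.

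| Subject | Infusion | Footnote a | Footnote c | Result |
|---|---|---|---|---|
| Single dose, C1D1 and C1D8 both tolerated | C1D15 on | 100 | 100 allowed | Agree |
| Single dose, C1D1 tolerated, C1D8 not | C1D15 on | 100 | 100 not allowed | **Conflict** |
| Single dose, C1D1 not tolerated | C1D15 on | condition not met | 100 not allowed | No conflict |
| Split dose, C1D8 tolerated | C1D15 | 100, if footnote a covers split dosing | not allowed (only one 16 mg/kg infusion so far) | Conflict on that reading |
| Single dose, C1D1 tolerated | C1D8 | 100, if C1D8 counts as subsequent | not yet allowed; row gives 50 | Conflict on that reading |

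Only the second line needs no choice of reading.

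**Step 2. Count the infusions in the firm case.** From the schedule in Section 4.1.4.2, starting at C1D15:

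- Cycle 1: Days 15 and 22 = 2
- Cycle 2: weekly = 4
- Cycles 3 to 6: 4 × 2 = 8
- Total through Cycle 6: 2 + 4 + 8 = 14, then one every 4 weeks from Cycle 7

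All 14 are affected if footnote c means literally the first two infusions, because its condition can then never be met. If any two tolerated infusions would do, a tolerated C1D15 satisfies it and only C1D15 itself is affected.

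**Step 3. Size of the rate difference.** The dilution is 500 mL. For single dosing, Section 4.1.3 states: "Daratumumab infusion solution will be prepared as a 1,000-mL (first dose, unless using split dose) or 500-mL (second and subsequent doses) dilution". For split dosing it states: "The dilution will be in 1000 cc of normal saline until the subject completes an infusion without > Grade 1 IRR". A split-dose subject who tolerated C1D8 is therefore also at 500 mL by C1D15.

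- Concentration: 16 / 500 = 0.032 mg/kg per mL
- First hour at 50 mL/hour: 50 × 0.032 = 1.6 mg/kg
- First hour at 100 mL/hour: 100 × 0.032 = 3.2 mg/kg

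For comparison, the hourly dose at the 200 mL/hour maximum:

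- Single-dose C1D1 in 1000 mL: 200 × 16/1000 = 3.2 mg/kg per hour
- C1D8 in 500 mL: 200 × 0.032 = 6.4 mg/kg per hour

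**Step 4. Uninterrupted time for 500 mL.**

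- Start at 50: 50 + 100 + 150 + 200 = 500 mL in 4.0 h
- Start at 100: 100 + 150 + 200 = 450 mL in 3 h, then 50 / 200 = 0.25 h, total 3.25 h
- Difference: 0.75 h, or 45 minutes

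**The case against.** **The manual governs.** The protocol defers to the USPI/pharmacy manual in more than one place and promises sites further administration guidance. That may well settle practice. The deferral names the controlling document but does not reconcile the two printed rules, and Section 4.1.4.2 still directs sites to the table. The manual is not available here, so what it says cannot be assumed.

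**Footnote c is the natural controlling text.** It sits on the row a site would read from C1D15 onward and is worded as a restriction. This has force, and it is why the stricter rule is the sensible default. But footnote a is worded as a directive, and nothing in the protocol ranks one footnote above the other.

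**Footnotes a and b may be parallel rules, one for single and one for split dosing.** This stands. Footnote a does not limit itself to single dosing, but both footnotes hang on the C1D8 row and can be read as alternatives. A reader might infer that split-dose subjects certainly face a contradiction at C1D15; the text permits that reading without requiring it. Likewise, the clash with the 50 mL/hour C1D8 row goes away if footnote a means only infusions after C1D8, as the separate row and the introductory text suggest.

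**The exposure difference is small.** This also stands. It concerns the first hour, at hourly doses the schedule already allows at C1D1 and C1D8, and Section 3.4.1.4 requires interruption for a reaction of any grade.

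**Conclusion.** The inconsistency is real, and in one case it is firm: single dosing, C1D1 tolerated, C1D8 not tolerated, from C1D15 onward. It covers 14 scheduled infusions through Cycle 6, and the 4-weekly infusions after that, if footnote c is taken literally. The split-dose and C1D8 conflicts are conditional on how footnote a is read. The 100 mL/hour start is taken to be what footnote c calls modified, because that footnote is attached to the 100 mL/hour row and the table shows no other modified rate.

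Two stronger inferences are not supported:

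- A reader might suppose that every subject who reacts early is affected. A subject who fails the first 16 mg/kg infusion meets neither footnote's condition, so the two do not collide.
- A reader might suppose that reaction rates, endpoints or the comparison between arms are biased. The documents give neither split-dose uptake nor tolerance by infusion, and do not show which footnote sites follow. The number of subjects affected, and any consequence for results, cannot be estimated.

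This is a minor safety-wording correction to a dosing instruction.

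**What to change.** Check the table against the current USPI/pharmacy manual that the protocol cites, then issue one administrative letter so that the table states a single rule.

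- **Unless the manual specifies otherwise**, use the stricter rule. Delete footnote a or align it with footnote c. Start C1D8 at 50 mL/hour and allow 100 mL/hour only after two tolerated 16 mg/kg infusions. State that 50 mL/hour applies until then, which is at present only implied. Say whether the two must be the first two or may be any two.
- **If the manual differs**, conform both footnotes to it.
- **In either case**, do not raise the starting rate straight after an infusion that was not tolerated.

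The cost is the letter plus about 45 minutes more chair time per affected infusion, relative to following footnote a. Under the stricter rule with footnote c kept literal, a subject in the firm case would spend at most 14 × 0.75 = 10.5 extra hours through Cycle 6, with a further 0.75 hours per 4-weekly infusion afterwards. Accepting any two tolerated infusions could reduce this to a single 0.75 hours.

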4.1.4.3 Pomalidomide in the ND-Pd Cohort (Cohort A)

Pomalidomide will be administered orally at the dose of 4 mg daily on Days 1 - 21 of each 28-day cycle. Pomalidomide should be taken without food (at least 2 hours before or 2 hours after a meal).

Subjects should be instructed that if a dose of pomalidomide has been missed and it has been less than 12 hours since the subject's regular dosing time, to take pomalidomide as soon as the subject remembers. If it has been more than 12 hours, the dose must be skipped. Subjects should not take 2 doses at the same time.

4.1.4.4 Dexamethasone in the ND-Pd Cohort (Cohort A)

At the investigator's discretion, the oral dexamethasone dose may be given as a split dose over 2 consecutive days each week.

The administration of dexamethasone is summarized in [Table 4.1.4.4-1](#).

Table 4.1.4.4-1: Dexamethasone Dosing

Age	Day 1	Day 8	Day 15	Day 22
Cycles 1-2				
≤ 75 years old	20 mg IV before daratumumab infusion 20 mg PO after daratumumab infusion			
> 75 years old	16 mg IV before daratumumab infusion 4 mg PO after daratumumab infusion			
Cycles 3-6				
≤ 75 years old	20 mg IV before daratumumab infusion 20 mg PO after daratumumab infusion	40 mg PO	20 mg IV before daratumumab infusion 20 mg PO after daratumumab infusion	40 mg PO
> 75 years old	16 mg IV before daratumumab infusion 4 mg PO after daratumumab infusion	20 mg PO	16 mg IV before daratumumab infusion 4 mg PO after daratumumab infusion	20 mg PO
Cycle 7 and Beyond				
≤ 75 years old	20 mg IV before daratumumab infusion 20 mg PO after daratumumab infusion	40 mg PO	40 mg PO	40 mg PO
> 75 years old	16 mg IV before daratumumab infusion 4 mg PO after daratumumab infusion	20 mg PO	20 mg PO	20 mg PO

On weeks with daratumumab infusion, dexamethasone will be administered as a split dose as described in Table 4.1.4.4-1. The IV dose can be administered approximately 1 hour prior to every daratumumab infusion (can be administered before nivolumab infusion).

On weeks without daratumumab infusion, dexamethasone will be administered orally only as described in Table 4.1.4.4-1.

If daratumumab dosing is skipped or discontinued, dexamethasone will be administered orally as in weeks without daratumumab.

